7.4.1. Sensitivity Analysis of Primary Efficacy Variable

The following sensitivity analysis will be performed for the primary endpoint to explore the robustness of inferences from the main estimator:

• Tipping point analysis (MNAR): The tipping point assumption will be used, i.e., after the first visit with missing data, the trajectories of the subjects in the NBI-1065846 group are assumed to be worse by an amount of delta. After the MI, as defined previously, an amount of delta will be added to each imputed value at Day 57 in the NBI-1065846 group. Successively harsher deltas will be imposed on the imputed values in the NBI-1065846 group, starting with a DARS total score decrease (worsening) of -1. The delta is further decreased in the steps of 1 (ie, -1, -2, -3, ...) until the statistical significance is lost, ie, until the p-value becomes ≥0.1. For the control group, the MI using MAR assumption will be used.

7.4.2. Supplementary Analysis of Primary Efficacy Variable

The following supplementary analyses will be performed for the primary efficacy endpoint:

- Completers analysis using all subjects in the Efficacy Analysis Set with non-missing data for the primary endpoint at the Day 57 visit
- COVID-19 impact analysis excluding all subjects who discontinued study treatment dosing prematurely due to COVID-19.

Neurocrine Biosciences, Inc. Statistical Analysis Plan Study NBI-1065846-MDD2020 16August2023

7.5. Secondary Efficacy Endpoints

7.5.1. Change in total MADRS score from baseline to Day 57 in subjects with moderate or higher severity depression

The MADRS is a 10-item diagnostic questionnaire that psychiatrists use to measure the severity of depressive episodes in subjects with mood disorders. Higher MADRS scores indicate more severe depression, and each item yields a score of 0 to 6.

The MADRS total score will be calculated as the sum of the 10 individual item scores, which ranges from 0 to 60. If more than two individual items are missing, the MADRS total score will not be calculated and will be left as missing. If less than or equal to two individual item scores are missing, the missing item scores will be imputed by the mean of all other available item scores, or the maximum possible values for the missing responses, whichever is smaller, to calculate the MADRS total score.

Descriptive statistics will be presented by treatment group for observed total MADRS score, and changes from baseline at each visit will be presented by treatment group for subjects with moderate or higher severity depression, which is defined as baseline HAM-D17 score ≥19. The changes from baseline to Day 57 will be analyzed using ANCOVA. The ANCOVA model will be similar to the model described above for the primary endpoint analysis.

7.5.2. Change in CGI-S score from baseline to Day 57

The Clinical Global Impression - Severity (CGI-S) uses a 7-point Likert scale to rate the severity of the subject's illness at the time of assessment, relative to the clinician's past experience with subjects who have the same diagnosis. Considering total clinical experience, a subject is assessed on severity of mental illness at the time of rating as 1=normal, not at all ill; 2=borderline mentally ill; 3=mildly ill; 4=moderately ill; 5=markedly ill; 6=severely ill; and 7= extremely ill.

Number and percentage of subjects by CGI-S categories will be summarized by treatment group and visit. In addition, the shift table for CGI-S categories from baseline to Day 57 will be presented.

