11.4.2. Secondary

- Change in total MADRS score from baseline to Day 57 in subjects with moderate or higher severity depression.
- Change in CGI-S score from baseline to Day 57.

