4.2. Secondary Efficacy

- Change in total Montgomery Asberg Depression Rating Scale (MADRS) score from baseline to Day 57 in subjects with moderate or higher severity depression.
- Change in Clinical Global Impression-Severity (CGI-S) score from baseline to Day 57.

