7. EFFICACY

The efficacy endpoints and planned analysis methods are described below. Unless otherwise specified, the Full Analysis Set will be used for the primary analyses of all efficacy endpoints. Descriptive statistics will be presented by treatment group according to the study visit. Continuous secondary efficacy endpoints will be analyzed using a similar ANCOVA model as described for the primary endpoint; categorical and ordinal secondary endpoints will be analyzed using the Cochran-Mantel-Haenszel (CMH) Chi-square test adjusted for illness severity (stratification factor) and use of concomitant antidepressant medication(s) at time of randomization.

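### Change in CGI-S, the only secondary efficacy endpoint covering all randomised subjects, has no planned treatment difference or CI, and the test that appears to apply does not adjust for baseline CGI-S

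*SAP*

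**What the plan says.** SAP 4.2 lists "Change in Clinical Global Impression-Severity (CGI-S) score from baseline to Day 57" as a secondary endpoint, and Protocol 11.4.2 agrees ("Change in CGI-S score from baseline to Day 57"). The other secondary endpoint, change in MADRS, is limited to subjects with baseline HAM-D17 of 19 or more (SAP 7.5.1).

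SAP 7.5.2 describes the instrument, which "uses a 7-point Likert scale to rate the severity of the subject's illness", and then plans two displays. The first is "Number and percentage of subjects by CGI-S categories will be summarized by treatment group and visit". The second is that "the shift table for CGI-S categories from baseline to Day 57 will be presented". The section names no test, model, contrast, interval or rule for a missing Day 57 rating.

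The opening of SAP 7 sets the general rule. Continuous secondary endpoints get an ANCOVA similar to the primary one, while "categorical and ordinal secondary endpoints will be analyzed using the Cochran-Mantel-Haenszel (CMH) Chi-square test", adjusted for the HAM-D17 severity stratum "and use of concomitant antidepressant medication(s) at time of randomization". Protocol 11.5.1.3 makes the same split without naming adjustment factors.

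**The concern.** The endpoint is defined as a change in score, but its own section treats it only as categories. Read with SAP 7, the likely analysis is a stratified CMH test. That test would give a p-value, with no planned estimate of how far apart the arms are. It would also make no adjustment for the baseline CGI-S rating taken on Day 1.

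The secondary objective concerns depression symptoms in subjects with MDD generally, and CGI-S is the only listed secondary efficacy endpoint that speaks to all of them. This is a proof-of-concept study with nominal p-values (SAP 7.1), so an estimate with an interval is the most useful output. The SAP also leaves open which rule applies, which CMH statistic is meant, and whether the response is the Day 57 category or the change. SAP 1 says that decisions on the final analysis will be documented in the SAP before unblinding.

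**Working it through.** **The plan's own figure.** SAP 3.3 and Protocol 11.2 give 88 randomised 1:1, 85% completing, effect size 0.5, one-sided 0.1, and about 80% power. Completers: 0.85 × 88 = 74.8, or 37.4 per arm. Power = Φ(0.5 × √(37.4/2) − 1.2816) = Φ(2.162 − 1.282) = 81%. The figure reproduces, but it is for DARS. The documents give no effect size, SD or power for CGI-S, so what follows is illustration.

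**Which rule applies.**
- For ANCOVA: the endpoint is worded as a change in score (SAP 4.2, Protocol 11.4.2).
- For CMH: 7.5.2 describes a 7-point Likert scale and plans only category displays.
- CMH is the more natural reading, but no text assigns it. It would have 3 × 2 = 6 strata.

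**Size without stratification.** Let r be the baseline-to-Day 57 correlation (assumed), with equal SDs. Relative variances are 1 for the Day 57 score, 2(1 − r) for the change, and 1 − r² for ANCOVA with baseline CGI-S.

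| r | ANCOVA ÷ Day 57 score = 1 − r² | ANCOVA ÷ change = (1 + r)/2 |
|---|---|---|
| 0.3 | 0.91 | 0.65 |
| 0.5 | 0.75 | 0.75 |
| 0.6 | 0.64 | 0.80 |
| 0.7 | 0.51 | 0.85 |

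For r from 0.3 to 0.6 this is 9-36% less variance than the Day 57 score alone, and 20-35% less than the change. These figures overstate the gain over the planned test. If v (at most 1) is the share of baseline CGI-S variance left within strata, and the strata act on Day 57 only through baseline, the ratios become (1 − r²)/(1 − r² + r²v) and (1 − r²)/(1 − r² + (1 − r)²v). Both move towards 1 as v falls.

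**Size against a stratified CMH.** A simulation used:
- 75 subjects, six strata, severity shares 10/50/40%, and 60% on antidepressants;
- scores rounded to the 1-7 scale;
- a true effect of 0.5 SD and one-sided 0.1;
- the row-mean-score form of CMH;
- 4,000 trials per row for power (standard error near 80%: √(0.8 × 0.2/4000) = 0.6 points).

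All of these are assumptions except the six strata, the 1-7 scale, the 0.1 level and the number of completers (74.8 rounded to 75). The 0.5 is borrowed from the primary endpoint.

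| r | HAM-D17 to baseline CGI-S correlation | CMH, Day 57 score | CMH, change | ANCOVA with baseline |
|---|---|---|---|---|
| 0.3 | 0.3 | 77.5% | 65.5% | 79.4% |
| 0.3 | 0.6 | 77.6% | 66.6% | 79.4% |
| 0.5 | 0.3 | 76.5% | 73.8% | 83.5% |
| 0.5 | 0.6 | 79.1% | 76.6% | 83.9% |
| 0.7 | 0.3 | 78.8% | 86.4% | 92.1% |
| 0.7 | 0.6 | 81.2% | 86.6% | 90.9% |

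By subtraction, ANCOVA gains 2 to 13 points over CMH on the Day 57 score and 4 to 14 points over CMH on the change. At every r the gain is smaller when HAM-D17 tracks baseline CGI-S more closely. With no true effect (2,000 trials per row), rejection was 8.8-11.0% for all three methods, in line with the nominal 10%.

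**Missing Day 57 ratings.** SAP 5.1 says imputation is generally not done unless an endpoint subsection specifies it, and 7.5.2 specifies none. At 85% completion, 0.15 × 88 ≈ 13 subjects would drop out of the test, although the Full Analysis Set keeps all randomised subjects (SAP 5.2).

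**The case against.** The best defence is that SAP 7 governs every subsection and gives each secondary endpoint a test, so 7.5.2 merely adds displays. That stands: a reader of 7.5.2 alone might infer that no between-arm comparison is planned, and that would be wrong. If CGI-S change is read as continuous, SAP 7 already gives an ANCOVA similar to the primary one, and most of the complaint falls away. That is also fair, but the SAP does not say so and 7.5.2 leans the other way.

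Three stronger readings are tempting and should not be adopted.
- One might say that the CMH ignores baseline CGI-S. If the response is the change, baseline enters by subtraction; the accurate statement is that the test does not adjust for it.
- One might say that MADRS gets better handling of missing data. SAP 7.5.1 specifies only item-level imputation, and the multiple imputation steps in SAP 7.4 are written for DARS.
- One might quote the 9-36% or 20-35% variance reductions as the gain. They rest on assumed correlations and compare with unstratified analyses, not the planned test.

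A stratified CMH is also a legitimate test for a single ordinal item, and the category percentages by arm let a reader see roughly how large a difference is. What they lack is a single estimate with an interval.

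**Conclusion.** The point holds as a cheap improvement, not as an error that threatens a conclusion. A named secondary endpoint has no planned treatment difference or CI, its analysis rule and response are not stated, and the test its wording points to leaves baseline CGI-S unadjusted. A reader might infer an invalid test or inflated type I error; the documents support neither. Randomisation protects the comparison, p-values are nominal, and the documents attach no decision rule to CGI-S.

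The precision loss ranges from about 2 to 14 points of power in the illustration, depending on the response used, the assumed correlation (0.3 to 0.7) and how closely HAM-D17 tracks CGI-S. It also assumes a 0.5 SD effect, the row-mean-score CMH, and no effect of antidepressant use on CGI-S. The missing estimate and CI do not depend on any of these assumptions.

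**What to change.** In SAP 7.5.2, state that change in CGI-S at Day 57 will be analysed by ANCOVA with treatment, severity stratum, antidepressant use at randomisation and baseline CGI-S, and that the LS mean difference will be reported with a CI at a stated level. Keep the stratified CMH alongside as the ordinal check, specifying row mean scores and its response variable, and keep the category counts and shift table.

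Name the handling of missing Day 57 ratings explicitly, for example the multiple imputation procedure of the primary analysis. A cross-reference to MADRS would not settle it.

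The cost is a few sentences and one more table. The downside is that the ANCOVA treats a 7-point item as numeric, which is why the CMH should stay.

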7.6. Other Efficacy Endpoints

Status: Approved

Neurocrine Biosciences, Inc. Study NBI-1065846-MDD2020 Statistical Analysis Plan 16August2023 7.6.2. 7.6.3. 7.6.4. 7.6.5. 7.6.6.

Neurocrine Biosciences, Inc. Statistical Analysis Plan Study NBI-1065846-MDD2020 16August2023

7.6.7. Examination of subgroups

The following subgroups will be used to examine consistency of effect for the primary efficacy endpoint:

- Demographics (age groups [<35 years, ≥35 to <50 years, and ≥50 years], sex, and race)
- Baseline HAM-D17 score (≤ 7 vs. 8 to 18 vs. ≥19)
- Baseline HAM-D17 score (<22 vs. ≥22)
- Baseline total MADRS score (≤ 23 vs. 24 to 27 vs. ≥28)
- Baseline MADRS Item 8 score (≤3 vs. ≥4)
- Baseline DARS score (<33th vs. 33th-66th vs. >66th centile)
- Baseline SHAPS score (<41 vs. ≥41)
- Use of antidepressants at baseline (Yes vs. No)
- Use of selective serotonin reuptake inhibitor (SSRI) (yes, no)
- Use of bupropion (yes, no)

Neurocrine Biosciences, Inc. Statistical Analysis Plan Study NBI-1065846-MDD2020 16August2023

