4. STUDY DESIGN

4.1. Overall Study Design

This is a Phase 2, randomized, double-blind, parallel-group, proof-of-concept study comparing use of NBI-1065846 with placebo for improvement of anhedonia in patients with MDD.

The study consists of a Screening Period of up to 28 days (Days -28 to -1), an 8-week Treatment Period (Days 1 to 57), and an 8-week Safety Follow-up Period (with visits at 4 and 8 weeks [Days 78 and 106] after last dose of study treatment).

Approximately 88 subjects are planned to be enrolled in the study. Eligible subjects include patients with MDD who have been treated with antidepressant medication(s) and who continue to have anhedonia (Snaith-Hamilton Pleasure Scale [SHAPS] ≥30 [Krystal et al., 2020; Trostheim et al., 2020]). Subjects currently receiving antidepressant medication(s) must be receiving them for ≥8 weeks prior to screening at or above the therapeutic dose based on the Massachusetts General Hospital - Antidepressant Treatment Response Questionnaire (MGH-ATRQ). Subjects not currently receiving pharmacological treatment for depression must have received ≥1 antidepressant medication(s) at a therapeutic dose per MGH-ATRQ for ≥8 weeks in the current or most recent episode of depression. To ensure adequate representation of subjects across ranges of depression severity, the Sponsor may add limits to prevent further enrollment in specific subgroups based on Hamilton Depression Rating Scale-17 Item (HAM-D17) scores at baseline.

Study treatment will be administered as monotherapy or as an adjunctive treatment to the subject's current oral antidepressant medication(s); subjects receiving antidepressant medication(s) at screening are expected to continue using them at the same dose throughout the study.

Subjects will be randomized in a 1:1 ratio in a double-blinded fashion to receive either NBI-1065846 or placebo, administered on a weekly basis, for a period of 8 weeks. The randomization will be stratified based on the Hamilton Depression Rating Scale-17 Item (HAM-D17) score at baseline: remission (HAM-D17 \leq 7), mild illness (HAM-D17 from 8 to 18), and moderate to severe illness (HAM-D17 \geq 19) (Zimmerman et al., 2013).

The end-of-study will be the last scheduled visit assessments of the last subject or last scheduled procedure shown in the schedule of assessments (Table 8) for the last subject in the study.

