3.3. Sample Size Considerations

Assuming that 85% of the 88 subjects (randomized in a 1:1 ratio to NBI-1065846 and placebo groups) complete the Day 57 assessment, the study has approximately 80% power to detect an effect size of 0.5 for the primary endpoint at 1-sided significance level of 0.1.

Neurocrine Biosciences, Inc. Statistical Analysis Plan Study NBI-1065846-MDD2020 16August2023

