7.4. Primary Efficacy Endpoint

The DARS is a dynamic scale that measures desire, motivation, effort and consummatory pleasure across hedonic domains. The DARS is a self-report questionnaire that measures anhedonia across 4 domains: hobbies/pastimes, food/drinks, social activities, and sensory experiences. The DARS is rated on a five-point Likert scale from 0 (not at all) to 4 (very much), higher values indicating less anhedonia. All items are summed up to a total score in the range of 0 to 68.

Descriptive statistics will be presented by treatment group for the DARS total score observed values, and changes from baseline at each visit. The primary endpoint will be analyzed using the Full Analysis Set by comparing NBI-1065846 and placebo using an Analysis of Covariance (ANCOVA) model. The model will include treatment group, illness severity (stratification factor), use of concomitant antidepressant medication(s) at time of randomization ([ie, yes vs no], covariate), and baseline DARS score (covariate).

Subjects who are missing DARS score at Day 57 will have their data imputed through a multiple imputation (MI) procedure. Missing data will be imputed for subjects in the NBI 1065846 treatment group using retrieved data (i.e., observed data from subjects who discontinued study drug) in that same treatment group, provided there is sufficient retrieved data. Otherwise, missing data will be imputed using observed data from subjects in the placebo treatment group, missing data will be imputed using observed data from subjects in the placebo treatment group. The details of imputation method are described below:

Step 1: For subjects with intermittent missing values, a monotone missingness pattern will be generated by imputing for the intermittent missing values using the Markov Chain Monte Carlo (MCMC) method, which assumes a multivariate normal distribution among all variables included in the imputation model. The MI procedure using SAS® software will be employed for this purpose and this first MI step is planned to be repeated 100 times, creating several different datasets with a monotone missing data structure. The imputation is based on the missing at random (MAR) assumption, i.e., the missing data are assumed to follow the

Neurocrine Biosciences, Inc. Statistical Analysis Plan Study NBI-1065846-MDD2020 16August2023

Status: Approved

same model as the other subjects in their respective treatment arm.

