Comparison of NBI-1065846 vs. placebo at each visit will be performed by constructing linear contrasts (or equivalent programming code) for differences between treatment group least-squares (LS) means. The LS means and differences in LS means will be presented in summary tables, along with the associated 90% confidence intervals. The treatment difference for the primary endpoint (Day 57) for NBI-1065846 vs placebo will be considered statistically significant if the one-sided nominal p-value is <0.1. Nominal p-values for comparing treatment groups at the individual postbaseline visits will also be reported in the summary tables.

An example of the SAS® software code for the ANCOVA model is provided below:

Version: 1.0 Status: Approved

Neurocrine Biosciences, Inc. Statistical Analysis Plan Study NBI-1065846-MDD2020 16August2023

To convert the two-sided p-values into one-sided p-value, if the treatment difference for NBI-1065846 vs placebo is in the positive direction, the one-sided p-value equals half of the two-sided p-value; if the treatment difference for NBI-1065846 vs placebo is in the negative direction, the one-sided p-value equals one minus half of the two-sided p-value.

Subgroup analyses for the primary efficacy endpoint will be performed for factors defined in Section 7.6.7 using an ANCOVA model, which will be similar to the model described above for the primary endpoint analysis, including additional fixed factors for the subgroup variable and the interaction between the treatment group and subgroup variable. Nominal two-sided p-values for comparing treatment groups and the associated 95% confidence intervals will be reported in summary tables and a forest plot, and p-values for the interaction term between treatment groups and each subgroup variable will be presented. This study was not designed to detect treatment differences with high statistical power within subgroups. No formal statistical testing will be conducted for subgroup analyses; p-values are nominal and intended to be interpreted in a descriptive manner.

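### SAP 7.4 and 7.6.7 look for effect modification by baseline scores only through bands; adding a treatment-by-continuous-score interaction would recover power if modification is roughly linear

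*SAP*

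**What the plan says.** SAP 7.6.7 lists the baseline variables used to check consistency of the primary effect. Each numeric score is cut:

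- HAM-D17 at 7/18, which are the randomization strata, and again as "Baseline HAM-D17 score (<22 vs. ≥22".
- Total MADRS at 23/27.
- DARS in sample tertiles: "Baseline DARS score (<33th vs. 33th-66th vs. >66th centile".
- SHAPS as "Baseline SHAPS score (<41 vs. ≥41".
- Age at 35 and 50 years, and MADRS Item 8 at 3/4.

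SAP 7.4 fits the primary ANCOVA, "including additional fixed factors for the subgroup variable and the interaction between the treatment group and subgroup variable". It presents an interaction p-value for each subgroup variable, with two-sided nominal p-values and 95% intervals for the treatment comparisons. It sets no significance level for the interaction. It also says that the study was not designed for high power within subgroups, that subgroups are not formally tested, and that their p-values are descriptive.

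Baseline DARS already enters the primary ANCOVA as a covariate on its own scale. SAP 7.6.1 to 7.6.6 are blacked out, so the absence of a continuous interaction can be stated only for the readable text.

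**The concern.** The trial recruits from remission to moderate-to-severe depression and stratifies on HAM-D17. Protocol 4.1 lets the sponsor cap severity subgroups, with this aim: "To ensure adequate representation of subjects across ranges of depression severity". How the effect varies with baseline severity is therefore something that this proof-of-concept study could usefully inform.

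Banding treats everyone within a band as alike, and three bands spend two degrees of freedom. If the effect changes gradually with the score, this discards information that a small trial can ill afford. The result also depends on the cut. HAM-D17 is cut two ways and so yields two interaction p-values for one score, with no stated rule for reading them if they disagree. At stake is the quality of an exploratory consistency check, which may still guide the choice of population for a later trial.

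**Working it through.** **1. The plan's own figure.** SAP 3.3 takes 85% of 88 subjects as Day 57 completers. On that basis, "the study has approximately 80% power to detect an effect size of 0.5 for the primary endpoint at 1-sided significance level of 0.1". Completers: 88 × 0.85 = 74.8, or 37.4 per arm. Normal approximation: 0.5 × √(37.4/2) = 2.162; 2.162 − 1.282 = 0.880; Φ(0.880) = 81.1%. The noncentral t with 37 per arm gives 80.4%. The stated 80% reproduces. It is power for the main effect; the documents give none for any interaction.

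**2. Sample size for the interaction.** SAP 7.4: "Subjects who are missing DARS score at Day 57 will have their data imputed through a multiple imputation (MI) procedure". The model therefore runs on 88 subjects, of whom about 75 are expected to be observed. Both values are used.

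**3. Assumptions not in the documents.** Normal baseline score; residual SD 1; treatment effect changing linearly by g SD per SD of score; two-sided level 0.1 (the study's overall level) or 0.05 (matching the 95% subgroup intervals); illustrative band shares.

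**4. Formula.** For 1:1 allocation, the noncentrality of the interaction F-test is λ = (N/4) × g² × R. R is the share of score variance that lies between bands. R = 1 for the continuous score (1 df). For a normal score, R = 0.637 for a 50/50 split (1 df), 0.490 for 80/20 (1 df), 0.793 for tertiles (2 df) and 0.770 for 10/50/40 bands (2 df). Error degrees of freedom are about N minus 8 to 10.

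Example, N = 88 and g = 0.5: continuous λ = 22 × 0.25 = 5.50; 50/50 gives 5.50 × 0.637 = 3.50; 80/20 gives 2.70; tertiles give 4.36 on 2 df.

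**5. Interaction power (%), N = 88, two-sided 0.1:**

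| g | Continuous | 50/50 | 80/20 | Tertiles | 10/50/40 |
|---|---|---|---|---|---|
| 0.10 | 14 | 12 | 12 | 12 | 12 |
| 0.25 | 32 | 24 | 21 | 22 | 22 |
| 0.375 | 54 | 40 | 34 | 38 | 37 |
| 0.50 | 75 | 58 | 49 | 56 | 55 |

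For g from 0.25 to 0.5 the loss is about 8 to 26 points. Simulating the ANCOVA directly gives 7 to 28. With no interaction, both kinds of test reject in about 10% of simulated trials, so the gain is not bought with false positives.

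**6. Other settings, same g range and bands.** N = 88 at 0.05: about 6 to 27 points. N = 75 at 0.1: about 7 to 25. N = 75 at 0.05: about 5 to 25. Overall, about 5 to 28.

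**7. Weaker modifiers, N = 88, level 0.1.** By formula, g = 0.1 loses 1 to 2 points (near zero to 4 by simulation), g = 0.15 loses 3 to 4, and g = 0.2 loses 5 to 7.

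**8. Other shapes, by simulation, N = 88.** At level 0.1, with a 1 SD step exactly at the cut, the bands win: 74% against 57% for a median cut, and 57% against 34% for an 80/20 cut. At level 0.05 with a U-shape (g = 0.5), tertiles reach 14% against 7% for a linear term.

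**The case against.** The strongest reply is that the SAP already limits these analyses. They check consistency, are not formally tested, and no trial decision rests on them. That stands, and it makes this an optional improvement.

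Second, the size of the loss is assumed. A reader might take a fixed number of lost points as a property of this trial; the documents do not support that. Wider choices of N, level, slope and split (out to 90/10) move the loss for a linear modifier from about 2 to 46 points, and the sign can reverse. The upper slopes are also strong: with a mean effect of 0.5 SD and g = 0.5, the effect is zero at 1 SD below the mean score, negative below that (about 16% of subjects), and doubled at 1 SD above. Real scores will not be exactly normal either: SHAPS is cut off at 30 by inclusion criterion 5, and HAM-D17 groups may be capped.

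Third, a reader might conclude that the bands should become display only. That goes too far. A threshold effect is plausible in a population running from remission to severe illness, and there the bands do better. Protocol 4.1 cites a published severity classification for the 7/18 HAM-D17 cuts, which are the randomization strata. The cut at 19 also defines the population for the MADRS secondary endpoint (SAP 7.5.1).

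Finally, even the continuous test has only about 32% power at g = 0.25, so it would usually miss a modifier of that size.

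What survives is narrower: for graded modification the bands waste information already planned for collection, and the plan has no continuous analysis beside them.

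**Conclusion.** The point holds as a cheap improvement to a descriptive analysis. In the readable text, effect modification by these baseline scores and age is examined only by band. Under roughly linear modification of 0.25 to 0.5 SD per SD of score, with N of 75 to 88, the cost is about 5 to 28 points of interaction power (about 7 to 28 at a two-sided level of 0.1; the 5 comes from 75 subjects at 0.05). It shrinks to almost nothing for weak modifiers and becomes a gain for bands placed at a true step.

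A reader might infer that the primary result is weakened, or that the change would let the trial show reliably who benefits. Neither follows: the primary analysis is untouched, and interaction power stays modest either way.

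**What to change.** In SAP 7.4 and 7.6.7, for baseline HAM-D17, total MADRS, DARS, SHAPS and age, add the primary ANCOVA plus the continuous baseline value and its interaction with treatment. Baseline DARS needs only the interaction, since its main effect is already in the model. Include a simple curvature check, such as a treatment-by-squared-score term. Report the interaction p-value and the estimated treatment difference, with its interval, across the observed range, beside the planned banded results and forest plot.

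Keep the banded estimates and interaction for the HAM-D17 randomization strata. Name the continuous HAM-D17 interaction in advance as the main reading for that score, so that the extra split at 22 does not compete with it.

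The cost is a few sentences in the SAP and about five additional models, with no new subjects or assessments. The downside is a few more descriptive p-values, and a linear term that can miss step or U-shaped patterns. The retained bands would still show those patterns.
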